8.1.6 Dietary or Other Protocol Restrictions

No dietary restrictions related to tipifarnib are required. Subjects will be instructed to administer their dose of tipifarnib with a meal as the presence of food has been shown to improve the absorption of tipifarnib, as well as to reduce variability in the pharmacokinetic profile.

Tablets should be swallowed whole with water (~8 oz. or 250 mL). Tablets may be chewed or crushed if the Investigator deems it necessary. Use of a percutaneous endoscopic gastrostomy tube or nasogastric tube is allowed at the judgment of the Investigator.

Unless otherwise contraindicated, subjects should be advised to be appropriately hydrated during the course of the study (e.g. drinking at least 8 glasses of water/day).

8.1.6.1 Potential Effects on Reproduction and Development

Male and female fertility and reproductive capacity has been shown to be impaired in rats and additional details can be found in the Tipifarnib Investigator's Brochure.

In light of the observations in nonclinical testing, both female subjects and male subjects with female partners of child-bearing potential must agree to use a highly effective method of

contraception from the first dose of tipifarnib, during, and at least 4 weeks after last dose of trial medication. Female subjects of child-bearing potential must have a negative serum or urine pregnancy test within 72 hours prior to start of trial medication.

Additionally, since tipifarnib could induce toxicity of male reproductive organs and cause impairment of fertility, sperm cryopreservation should be recommended for male subjects wishing to preserve their fertility following tipifarnib treatment. Additionally, if the participant in the study is male, then the following items will be discussed with the subject:

- Prevention of pregnancy in a female partner
- Prevention of exposure of a partner to semen by any means (not just intercourse)
- Prevention of the possible exposure of a pregnant female to the study drug from semen.
- Informing their partner of the potential for harm to an unborn baby. The partner should know that if pregnancy occurs, she should promptly notify her personal doctor.
- Acceptable methods of birth control for male subjects while participating in this study and for 90 days after the last dose of the study drug:
 - Abstinence (no sex)
 - Condom plus spermicidal agent (foam gel/cream/film/suppository)

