administered at least 2 weeks prior to C1D1. Subjects must have recovered to NCI CTCAE v5.0 < Grade 2 from all acute toxicities (excluding Grade 2 toxicities that are not considered a safety risk by the Sponsor and Investigator) or toxicity must be deemed irreversible by the Investigator.

7. At least 2 weeks since last radiotherapy. Subjects must have recovered from all acute toxicities from radiotherapy.
8. ECOG performance status of 0-1 ([Appendix II](#)).
9. Acceptable liver function:
 - a) Bilirubin ≤ 1.5 times upper limit of normal (x ULN).
 - b) AST (SGOT) and ALT (SGPT) ≤ 1.5 x ULN.

The subject must meet/continue to meet these criteria at the time of first dosing, as confirmed by analysis within 72 hours of C1D1.

10. Acceptable renal function with either serum creatinine ≤ 1.5 x ULN or a calculated creatinine clearance ≥ 60 mL/min using the Cockcroft-Gault or Modification of Diet in Renal Disease (MDRD) formulas.

The subject must meet/continue to meet these criteria at the time of first dosing, as confirmed by review of analysis performed within 72 hours of C1D1.

11. Acceptable hematologic status:
 - a) ANC ≥ 1000 cells/ μ L.
 - b) Platelet count $\geq 75,000$ / μ L.
 - c) Hemoglobin ≥ 8.0 g/dL.

The subject must meet/continue to meet these criteria at the time of first dosing, as confirmed by review of analysis performed within 72 hours of C1D1.

12. Female subjects must be:
 - a) Of non-child-bearing potential (surgically sterilized or at least 2 years post-menopausal); or
 - b) If of child-bearing potential, subject must use a highly effective method of contraception, such as combined (estrogen and progestogen containing) hormonal contraception associated with inhibition of ovulation, progestogen-only hormonal contraception associated with inhibition of ovulation, intrauterine device, intrauterine hormone-releasing system, bilateral tubal occlusion, vasectomised partner or sexual abstinence. Both females and male subjects with female partners of child-bearing potential must agree to use a highly effective method of contraception from the first dose of tipifarnib, during tipifarnib treatment, and at

least 28 days after last dose of tipifarnib for females and 90 days for males.
Female subjects must have a negative serum or urine pregnancy test within 72 hours prior to start of trial medication.

c) Not breast feeding at any time during the study.

13. Written and voluntary informed consent understood, signed and dated.

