 - b) If of child-bearing potential, subject must use a highly effective method of contraception, such as combined (estrogen and progestogen containing) hormonal contraception associated with inhibition of ovulation, progestogen-only hormonal contraception associated with inhibition of ovulation, intrauterine device, intrauterine hormone-releasing system, bilateral tubal occlusion, vasectomised partner or sexual abstinence. Both females and male subjects with female partners of child-bearing potential must agree to use a highly effective method of contraception from the first dose of tipifarnib, during tipifarnib treatment, and at least 28 days after last dose of tipifarnib for females and 90 days for males. Female subjects must have a negative serum or urine pregnancy test within 72 hours prior to start of trial medication.
 - c) Not breast feeding at any time during the study.
13. Written and voluntary informed consent understood, signed and dated.

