11.2.2 Pregnancy and In Utero Drug Exposure

Only pregnancies considered by the Investigator as related to study treatment (e.g. resulting from a drug interaction with a contraceptive medication) are considered as AEs. However, all pregnancies with an estimated conception date during the study safety period must be recorded by convention in the AE page/section of the eCRF. The same rule applies to pregnancies in female subjects and in female partners of male subjects. The Investigator must notify the Sponsor in an expedited manner of any pregnancy using the Pregnancy Report Form, which must be transmitted according to the same process as described for SAE reporting.

Investigators must actively follow up, document and report on the outcome of all these pregnancies, even if the subjects are withdrawn from the study. The Investigator must notify the Sponsor of these outcomes using the Pregnancy Report Form, and in case of abnormal outcome, the Adverse Event Report Form when the subject sustains an event and the Parent-Child/Fetus Report Form when the child/fetus sustains an event.

Any abnormal outcome must be reported in an expedited manner, while normal outcomes must be reported within 45 days from delivery.

In the event of a pregnancy in a subject occurring during the course of the study, the subject must be discontinued from study medication immediately. The Sponsor must be notified without delay and the subject must be followed as mentioned above.

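### Section 8.1.6.1 gives men a 4-week contraception minimum after the last dose, 62 days short of the 90 days required elsewhere in the protocol

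*Protocol*

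**What the plan says.** Four places in the protocol set a period of contraception after the last dose of tipifarnib.

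- **Section 8.1.6.1, mandatory sentence.** It binds women, and men whose female partners could conceive, to the same rule: "contraception from the first dose of tipifarnib, during, and at least 4 weeks after last dose of trial medication". There is one period, with no split by sex.
- **Section 8.1.6.1, list for men.** The section goes on to say that "if the participant in the study is male, then the following items will be discussed with the subject". The last item in that list reads "Acceptable methods of birth control for male subjects while participating in this study and for 90 days after the last dose of the study drug".
- **Synopsis, AIM-HN inclusion criterion 12b.** It separates the sexes: "least 28 days after last dose of tipifarnib for females and 90 days for males".
- **Section 7.1.1, inclusion criterion 12b.** The same rule is repeated: "at least 28 days after last dose of tipifarnib for females and 90 days for males".

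**The concern.** The sentence in Section 8.1.6.1 exists to state the required minimum, and for men it states the wrong one. A man who stops contraception on day 29 after his last dose complies with it and breaches criterion 12b.

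This is an operative reproductive-safety rule, not background text. The same section warns of toxicity to male reproductive organs, of exposing a pregnant partner through semen, and of harm to an unborn child. Nothing in the protocol gives a reason for a shorter male period.

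Three features of the layout make the slip easier to act on:

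- In criterion 12 the male period sits under a heading that speaks only of female subjects. Someone looking for the rules for men would naturally turn to Section 8.1.6.1.
- Within Section 8.1.6.1 the short period carries the obligation. The 90 days appears only inside a bullet on acceptable methods, in a list of discussion items.
- The End of Treatment visit falls about 30 days (± 7) after the last dose, or earlier if new therapy starts (Section 9.2.7). A man working to 4 weeks could stop at about that visit. The later follow-up contacts collect survival and subsequent treatment (Section 9.2.9), with no contraception check listed.

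**Working it through.** No sample-size, power or error-rate figure is involved, so there is no design figure to reproduce. The check sets the four statements side by side and applies calendar arithmetic.

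| Place in the protocol | Women | Men |
|---|---|---|
| Section 8.1.6.1, mandatory sentence | at least 4 weeks | at least 4 weeks |
| Section 8.1.6.1, list for men | not covered | 90 days |
| Synopsis, criterion 12b | at least 28 days | 90 days |
| Section 7.1.1, criterion 12b | at least 28 days | 90 days |

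1. Convert to days: 4 weeks × 7 = 28 days.
2. Women: 28 − 28 = 0 days. The mandatory sentence and criterion 12b agree.
3. Men: 90 − 28 = 62 days. The mandatory sentence falls short of the other three statements by this amount.
4. As a proportion for men: 28 / 90 = 0.311, so the sentence states about 31% of the period given elsewhere.
5. Intended value: three statements give men 90 days and one gives 4 weeks. A man who uses contraception for 90 days satisfies all four. A man who uses it for 28 days satisfies only one.
6. Position of the gap: it runs from day 28 to day 90 after the last dose. Section 11.3.1 ends adverse event reporting at about day 30, or earlier if other anticancer therapy begins. At least about 90 − 30 = 60 of the 62 days therefore fall after routine safety reporting has closed.

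These figures measure the disagreement between passages. They are not an estimate of how many subjects or partners were exposed.

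**The case against.** The strongest reply is that the protocol already secures the 90 days. Every inclusion criterion must be met, and criterion 12b expressly reaches men with female partners of child-bearing potential. A correctly enrolled man has therefore agreed to 90 days before his first dose, and nothing in Section 8.1.6.1 releases him. The same section also requires the 90-day item to be discussed with him. To be misled, a site would have to overlook the entry criterion and stop reading partway through a short section.

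It is also fair to say that a stated minimum of 4 weeks is only a floor. The rules can all be met at once, so this is an understated minimum for one sex and not a pair of incompatible instructions. What subjects are actually told depends on the consent form, which was not available. The SAP (Section 3) refers to early closure of the study, so there may be few men left to benefit and perhaps no further amendment to carry the edit.

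All of this limits the practical risk, and it is accepted. None of it makes the male minimum in the mandatory sentence correct.

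Pregnancy reporting in Section 11.2.2 is a separate matter and no defect is shown there. Its recording rule refers to a safety period that it does not define ("all pregnancies with an estimated conception date during the study safety period must be recorded"), but it also says "The Investigator must notify the Sponsor in an expedited manner of any pregnancy using the Pregnancy Report Form", with no time limit stated.

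**Conclusion.** The point holds. The mandatory sentence in Section 8.1.6.1 sets a post-treatment contraception minimum for men of 28 days where the protocol otherwise requires 90, a shortfall of 62 days. For women there is no discrepancy. It is an internal inconsistency with a clear correct value.

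The conclusion rests on the protocol text alone. That 90 days is the intended male period is an inference from the other three statements and from the absence of any rationale for a shorter one. The risk to subjects and partners is confined to a site that applies the sentence in isolation. The direct benefit of a correction is to men still on treatment or within 90 days of their last dose. The statistical design and analysis are unaffected.

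**What to change.** In Section 8.1.6.1, replace the single 4-week period at the end of the mandatory sentence with the wording of criterion 12b: "at least 28 days after last dose of tipifarnib for females and 90 days for males". The female period does not change; the male minimum rises by 62 days to match the rest of the protocol. Section 11.2.2 needs no change for this purpose.

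The cost is one line of text. There is no new visit, procedure or assessment, and no change to eligibility, because criterion 12b already sets these periods. Section 4.5 requires a formal amendment with ethics committee review for any protocol change, so the edit is best carried with the next amendment.

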8.2 Monitoring of Subject Compliance

The importance of treatment compliance should be emphasized to the subject. Subjects will be given study drug and detailed instructions on how to take medications at home. Subjects will be instructed to return all used and unused study drug containers at each study visit. Subject compliance with the dosing schedule will be assessed by reconciliation of the used and unused study drug at each clinic visit and review of the dosing diaries. The quantity dispensed, returned, used, lost, etc. must be recorded on the dispensing log provided.

Compliance will be monitored and documented by site personnel on the appropriate form. The site personnel will question the subject regarding adherence to the dosing schedule by reviewing the dosing diaries, recording the number of tablets (and strengths, if applicable) returned, the date returned, and determining treatment compliance (at least 80% of the total assigned dose) before dispensing new medication to the study subject.

9 STUDY PROCEDURES

9.1 Pre-screening for HRAS Mutation

The pre-screening for HRAS mutation procedures to be performed in subjects enrolled in KO-TIP-007 are outlined in [Table 1](#).

Kura Oncology, Inc. or its designee will assign a subject number identifier for each subject that is enrolled into the study upon completion of informed consent for prescreening. Identification of HRAS mutations may be conducted using NGS gene panels that generate mutational information on tumor related genes, including variant allele frequency.

Screening for HRAS mutation can occur at any time prior to initiating tipifarnib treatment in this study and may be performed in subjects who are not yet fully eligible for KO-TIP-007, e.g. pre-screening for HRAS mutations may be performed in subjects currently receiving platinum-based or other 1st therapy. Because a tumor's biology changes over time and in response to anti-cancer therapies, it is recommended that testing is performed on tumor tissue obtained subsequent to the most recent prior; if it is not possible to obtain tissue meeting this criterion (clinical risks too high, patient refusal, etc), the reason must be documented. If several tumor samples are available, HRAS testing should be performed on the most recently obtained tumor sample.

Subjects are required to have a missense HRAS mutation for enrollment in AIM-HN, the tipifarnib treatment portion of KO-TIP-007. Subjects without a missense HRAS mutation may participate in SEQ-HN, the noninterventional portion of KO-TIP-007 (see [Section 9.1.4](#) and [Section 9.3](#)). Upon determination of subject HRAS mutational status, subject will proceed to cohort-specific screening procedures for participation in AIM-HN (HRAS mutant HNSCC subjects, [Section 9.2.1](#)) or SEQ-HN (HRAS wildtype HNSCC subjects, [Section 9.3.1](#)).

9.1.1 Subjects With Known HRAS Mutation

If a subject has had HRAS mutation testing as part of their medical care or through another study protocol, the following circumstances need to be considered prior to enrolment into the AIM-HN part of KO-TIP-007:

- If HRAS mutation data were obtained subsequent to the most recent prior therapy, and obtained using a Sponsor approved test, these data may be used for enrollment. Re-biopsy should be considered for tumor tissue not meeting this requirement. If re-biopsy is not possible, the clinical justification should be recorded. Procedures as outlined in [Section 9.1.2](#) regarding obtaining tumor material for potential confirmatory testing at a central laboratory should be followed.
- If HRAS mutation data were obtained using a test which is not approved by the Sponsor, these data may not be used for enrollment. In such cases, HRAS testing procedures outlined in [Section 9.1.2](#) should be followed for study eligibility.

In addition, the following procedures are to be performed in all subjects with known HRAS mutation status irrespective of method for previous HRAS testing:

- ICF for HRAS pre-screening: Subjects must be consented for study participation and should be documented in the subject's medical chart.

- Collection of a blood sample for the analysis of HRAS mutations [REDACTED] [REDACTED] in plasma and shipment to a Sponsor designated laboratory.
- Collection of HRAS mutation data including:
 - Anatomical biopsy site, date of sampling and setting (e.g. primary, locally advanced, metastatic lesion)
 - HRAS mutation in sample including variant allele frequency or HRAS wildtype status
 - Test platform (e.g. NGS, PCR, other)

9.1.2 Subjects Without Known HRAS Mutational Status: Testing for HRAS mutation at a Sponsor Designated Laboratory

The following procedures must be performed:

- ICF for HRAS pre-screening: Subjects must be consented for study participation and should be documented in the subject's medical chart.
- Collection and shipment of tumor material for HRAS mutation testing at a Sponsor designated laboratory. Additional details regarding HRAS testing procedures will be provided in a separate laboratory manual.
- Collection of a blood sample for the analysis of HRAS mutations [REDACTED] [REDACTED] in plasma and shipment to a Sponsor designated laboratory.
- Collection of HRAS mutation data including:
 - Anatomical biopsy site, date of sampling and setting (e.g. primary, locally advanced, metastatic lesion)
 - HRAS mutation in sample including variant allele frequency or HRAS wildtype status

9.1.3 Subjects Without Known HRAS Mutational Status: Local testing for HRAS mutation using a Sponsor approved test:

Subjects identified as HRAS mutant HNSCC using a Sponsor approved test used by the institution are eligible for enrollment in KO-TIP-007 based on the results of local HRAS testing.

In order to proceed with approved local testing, the following procedures must be performed:

- ICF for HRAS pre-screening: Subjects must be consented for study participation and should be documented in the subject's medical chart.

- Collection and shipment of tumor material, preferably from the same sample as was used for local testing, for HRAS mutation testing at the central laboratory during AIM-HN Screening. Additional details regarding HRAS testing procedures will be provided in a separate laboratory manual.
- Collection of a blood sample for the analysis of HRAS mutations [REDACTED] in plasma and shipment to a Sponsor designated laboratory.
- Collection of HRAS mutation data including:
 - Anatomical biopsy site, date of sampling and setting (e.g. primary, locally advanced, metastatic lesion)
 - HRAS mutation in sample including variant allele frequency or HRAS wildtype status
 - Test platform (e.g. NGS, PCR, other)

9.1.4 Subjects who have HNSCC without HRAS mutation

Subjects who are determined to be HRAS wildtype through prescreening testing in KO-TIP-007 will be offered participation in the SEQ-HN. Further details on the study procedures for subjects participating in SEQ-HN can be found in [Section 9.3](#).

9.2 AIM-HN

The evaluations to be performed for subjects enrolled in AIM-HN are summarized in [Table 2](#). The following subsections apply to subjects participating in AIM-HN.

9.2.1 Screening Procedures

A signed ICF must be obtained before any study-specific screening evaluations are performed and should be documented in the subject's medical chart. A separate consent will be obtained for HRAS mutation pre-screening procedures and is further detailed in [Section 9.1](#).

The following evaluations and procedures will be performed within 28 days prior to the first study drug administration (Cycle 1 Day 1):

- Signed ICF/ patient informed consent (PIC) and other forms required by local regulation (e.g. the Health Insurance Portability and Accountability Act (HIPAA)/Data Protection Act (DPA))
- Tumor assessments:
 - CT scan with a contrast agent is the preferred imaging method and the same technique should be used at baseline and post-treatment assessments. CT scan coverage at screening should encompass scans of the neck (including the skull base), chest and abdomen (including the liver and adrenals). Any other areas of disease involvement should be scanned based on the subject's signs and symptoms.

- The presence of at least one measurable target lesion per RECIST v1.1 must be confirmed by local radiology prior to enrollment. Subjects without at least one measurable target lesion confirmed by local radiology will not be enrolled into AIM-HN. Note: Confirmation of RECIST v1.1 measurable disease by local radiology is required for study eligibility.
- Transfer of baseline tumor scans, historical tumor scans (see below) and related clinical information to IRF.
 - Efforts should be made to obtain historical scans to document tumor progression. If additional time is needed to obtain the historical scans, these scans should be submitted no later than the first tumor response assessment (approximately 8 weeks following Cycle 1 Day 1). These historical scans should include the scans that demonstrate most recent progression that occurred on the prior regimen and the scan demonstrating the nadir prior to the progression. Confirmation of the prior progression will not be confirmed centrally, however these scans will be used by IRF for comparison of prior treatment effect with the baseline scans.
- Demographics
- Disease history including:
 - Primary diagnosis, date of initial diagnosis, stage of disease at diagnosis, anatomical disease site(s) at diagnosis
 - Current stage of disease
 - Smoking and betel nut exposure
 - Alcohol use
 - HPV status
 - Other relevant medical history
- First line systemic treatment for recurrent or metastatic HNSCC including:
 - Anatomical (organ) disease site(s) at the time of first line therapy for recurrent or metastatic disease
 - Performance status at the time of first line therapy for treatment of recurrent or metastatic disease.
 - Name of treatment
 - Dates of treatment (start, end).
 - Treatment outcome (response and response criteria), duration of response
 - Date of progression

- Prior cancer therapy(ies) for HNSCC including:
 - Name(s) of treatment(s), dates (start, end)
 - Treatment outcome (response and response criteria), duration of response
 - Date of progression(s).
 - Prior cancer surgery(ies) for HNSCC including date(s) of surgery.
 - Prior/current radiological treatments for HNSCC including anatomical site(s) and date(s) of radiation treatment.
- Buccal swab
- Collection and shipment of tumor material for HRAS mutation testing and pathology review at the central laboratory. Tumor material for central evaluation should preferentially be shipped by Cycle 1 Day 1. Additional details regarding central HRAS testing and pathology review procedures will be provided in a separate laboratory manual.
 - *Subject enrollment may be based on local pathology assessment and HRAS testing results from a Sponsor designated laboratory or Sponsor approved local tests.*
- Concomitant medications
- Assessment of AEs, including ongoing AEs

■ [REDACTED]

The following evaluations and procedures will be performed within 14 days prior to the first administration of study drug (Cycle 1 Day 1):

- Complete physical examination
- Height
- Weight
- Vital signs (heart rate, blood pressure, temperature)
- 12-lead ECG
- ECOG performance status.

■ [REDACTED]

- Laboratory tests: Fasting is not required.
 - Serum Chemistry
 - Hematology
 - Coagulation
 - Urinalysis

The following evaluations and procedures will be performed within 72 hours prior to the first administration of study drug (Cycle 1 Day 1):

- Serum/urine pregnancy test for females of child-bearing potential only
- Confirmation that the subject continues to meet laboratory prescribed eligibility criteria

If the subject meets all eligibility criteria after the screening visit(s), the study site will complete the inclusion/ exclusion criteria evaluation and submit the enrollment form to the Sponsor or designee.

9.2.2 Day 1 of Cycle 1

The following assessments will be conducted before the first dose of tipifarnib on Day 1 of Cycle 1:

- Collection of weight and vital signs (heart rate, blood pressure, temperature)
- ECOG performance status
- Symptom based physical examination
- Completion of Quality of Life assessment questionnaires
- Laboratory tests: Fasting is not required. Laboratory tests do not need to be repeated on Cycle 1 Day 1 if the laboratory tests to confirm continued subject eligibility were conducted within 72 hours prior to the first dose of tipifarnib, and upon review the tests confirm subject's continued eligibility for treatment.
 - Serum Chemistry
 - Hematology

Subjects will be administered the first dose of tipifarnib (600 mg) with food. Time of dosing is to be recorded.

The following assessments will be conducted after the first dose of tipifarnib on Day 1 of Cycle 1:

- [REDACTED]
- [REDACTED]
- [REDACTED]
- [REDACTED]

- Assessment of AEs
- Concomitant medications
- Subjects will continue to self-administer tipifarnib twice a day (approximately every 12 hours, same time every morning and evening) with a meal on days 1 – 7 and days 15 – 21

in 28-day treatment cycles (i.e. alternating week schedule). The interval between dosing should not be less than 8 hours.

9.2.3 Day 7 of Cycle 1

(required for Denmark only; all other regions should perform as clinically indicated)

Subjects should self-administer tipifarnib prior to the Cycle 1 Day 7 visit.

The following procedures will be performed at this visit:

- Serum Chemistry
- Hematology

9.2.4 Day 1 (± 2 days) of Cycle 2

Subjects should self-administer tipifarnib prior to the Cycle 2 Day 1 visit. [REDACTED]

The following procedures will be performed at this visit:

- Collection of weight and vital signs (heart rate, blood pressure, temperature)
- ECOG performance status
- Symptom based physical examination
- Completion of Quality of Life assessment questionnaires
- Laboratory Tests: Fasting not required.
 - Serum Chemistry
 - Hematology
 - Serum/urine pregnancy test for females of child-bearing potential only

[REDACTED]

[REDACTED]

[REDACTED]

[REDACTED]

- Concomitant medications
- Assessment of AEs

In addition to the above procedures, the clinical site will conduct a drug accountability review on the returned empty bottles and unused medications and will also review the dosing diaries to assess compliance with the dosing schedule.

